**The following Amendment(s) and Administrative Changes have been made to this protocol since the date of preparation:**

**Amendment No.** **Date:** **Admin. Change No.** **Date:**

---

---

---

## **PROTOCOL SYNOPSIS**

---

### **The prophylactic effect of Levosimendan in reducing acute kidney injury postoperatively in pediatric patients undergoing corrective heart surgery**

---

#### **Study centre(s)**

The Queen Silvia Children's Hospital, Department of anesthesia and intensive care unit

#### **Study period**

Estimated date of first subject enrolled: June 2014

Estimated date of last subject completed: June 2016

#### **Background**

Acute kidney injury (AKI) is a major cause of morbidity and mortality in critically ill patients including critically ill children. The etiology of AKI is multifaceted which may partly explain the lack of a causative therapy. The treatment of AKI remains supportive and consists of, in milder cases urine production enhancing medications, and in more severe cases renal replacement therapy. There is evidence that Levosimendan may protect the kidney from injury in conjunction with cardiac surgery in adults [1]. In this study we will use Levosimendan to intervene with renal hypoperfusion and assess its efficacy in reducing creatinine, which is used most frequently as a clinical marker of kidney injury. The study is prospective, randomized, and double-blinded. The trial will contain two study groups, 35 patients in each, where the one group will receive Levosimendan and the second group will receive Milrinone as an inotrope agent perioperatively. Milrinone is currently used as the drug of choice for inotropic therapy in our department like many other pediatric cardiac surgery centers. It remains to see if Levosimendan can exert a kidney protecting function in addition to its inotropic one.

**The aim** of the study is to assess the ability of Levosimendan to reduce the postoperative acute kidney injury in pediatric patients undergoing surgery for congenital heart disease (CHDs).

### **Primary objective**

The primary objective of this study is to investigate the preventive effect of Levosimendan on postoperative acute kidney injury in pediatric patients undergoing surgery for their CHDs. Creatinine levels postoperatively will be the primary endpoint.

### **Study design**

This is a parallel-group, prospective, randomized, double-blinded controlled study in pediatric patients in need for surgery due to their CHD.

A total of 70 male and female pediatric patients will be included in the study and undergo heart surgery according to routine procedures at the hospital. Patients will be randomly assigned to receive either Levosimendan (test group) or Milrinone (control group). Creatinine, the common marker of kidney injury, will be measured daily according to the clinical routines. The length of treatment (Levosimendan or Milrinone) is 24 hours. The treatment will be started during the operation at the same time-point at which Milrinone infusion routinely is started. Blood samples will be obtained at five occasions, during 24 hours perioperatively. Patients will be followed 4 days after termination of treatment.

### **Target subject population**

Young children, between the age of 1 to 12 months, with congenital heart disease in need of elective heart surgery

### **Inclusion criteria**

The inclusion criteria will be any of the diagnoses:

1. Non-restrictive VSD (corrective surgery)
2. Complete AVSD (biventricular repair)
3. Tetralogy of Fallot

### **Exclusion criteria**

The exclusion criteria will be

1. Unbalanced AVSD
2. Age less than one month and more than one year
3. Acute operation that is unscheduled operation during the first 24 hours after presentation to the department for thoracic surgery
4. Mild, moderate, or severe kidney dysfunction
5. Liver impairment or disease
6. Ongoing infection
7. Use of nephrotoxic drugs (like ibuprofen, angiotensin-converting-enzyme inhibitors, gentamicin, vancomycin) preoperative or postoperative until first post operative day
8. Use of inhibitors of membrane transport proteins (Cimetidine, cetirizine, trimethoprim, probenecid, rifampin and gemfibrosil)
9. Allergy to Levosimendan or substance included in the preparation or previous use of Levosimendan
10. Severe arrhythmias needing pace-maker treatment prior to the operation
11. Severe cardiac dysfunction needing treatment with extracorporeal membrane oxygenation (ECMO) prior to the operation
12. Severe uncorrected hypotension where the initiation of anesthesia is postponed for its correction
13. Re-operation

**Investigational product, dosage and mode of administration**

Active: Levosimendan 2.5 mg/mL solution, diluted to 0.05 mg/mL i.v.

Control: Milrinone i.v. standard of care

**Duration of treatment**

24 hours

**Duration of study**

30 days (24 hours treatment + 4 days follow up + 30-days-mortality registration)

### **Outcome variable(s):**

Creatinine is primary outcome in this study. Inflammatory biomarkers, NGAL, and other relevant biomarkers belong to secondary outcome variables.

### **Safety**

Adverse Events will be recorded. Serious Adverse Events will be reported.

### **Statistical methods**

The number of patients needed for the study will be 70 and is based on a 20% reduction in creatinine in the Levosimendan group compared with the Milrinone group postoperatively. The power of study is set on 80 %.

Patients will be randomly assigned to one of two treatment groups: Levosimendan (n=35) and Milrinone group (n=35).

Analysis of data will be performed by a professional statistician. Univariate analyses will be used where needed. Multivariable regression analysis will be used to identify association between the occurrences of AKI (based on creatinine results) and the measured clinical variables. Descriptive statistics will be applied on the secondary outcomes including clinical data (fluid balance, length of surgery, length of CPB, length of mechanical ventilation postoperatively, length of vasoactive therapy, number of vasoactive medications, total amount of infused vasoactive drugs, hemodynamic parameters).

Safety and tolerability data will be summarized descriptively by treatment and presented in tabular and/or graphical form. All adverse event data will be listed individually and summarized using MedDRA terminology.

## **LIST OF ABBREVIATIONS AND DEFINITION OF TERMS**

The following abbreviations and special terms are used in this study protocol.

Abbreviation or Explanation special term	
AE	Adverse event
AKI	Acute Kidney Injury
ARF	Acute Renal Failure
AVSD	Atrioventricular septum defect
CHDs	Congenital heart diseases
CPB	Cardiopulmonary bypass
CRF	Case report form
DAE	Discontinuation due to Adverse Event
EC	Ethics Committee, synonymous to Institutional Review Board (IRB) and Independent Ethics Committee (IEC)
ECG	Electrocardiogram
ECMO	Extracorporeal membrane oxygenation
GCP	Good Clinical Practice
ICU	Intensive care unit
ICH	International Conference on Harmonisation
KATP	Potassium-sensitive adenosine triphosphate channels
MMP-9	Matrix metalloproteinase-9
OAE	Other Significant Adverse Event (ie, adverse events of particular clinical importance, other than SAEs and those AEs leading to discontinuation of the subject from study treatment)
NGAL	Neutrophil gelatinase-associated lipocalin
PICU	Pediatric intensive care unit
SAE	Serious adverse event
SIRS	Systemic inflammatory response syndrome
SOPs	Standard Operating Procedures
SUSARs	Suspected unexpected severe adverse reactions
TOF	Tetralogy of Fallot
VSD	Ventricle septum defect

## **1. INTRODUCTION**

### **1.1 The importance of acute kidney injury**

Acute renal failure (ARF), which recently has been refined and defined as acute kidney injury (AKI), is a common and serious condition in critically ill pediatric and adult patients. Due to lack of standard definition of ARF the reported incidence of AKI has varied considerably, namely between 5 and 50% of critically ill patients, both children and adults. The morbidity and mortality of AKI is unacceptably high. The reported mortality rates of about 40-50% in dialysis-dependent AKI, demonstrates the seriousness of the condition. AKI is an independent factor for mortality in critically ill patients, meaning that the patients do not simply die with AKI but also from AKI. The treatment is supportive in addition to reversing the underlying causes. The supportive measures include optimizing fluid and cardiorespiratory status, avoiding nephrotoxic medications and renal replacement therapy [2].

### **1.2 Etiology of AKI**

It is well known that cardiopulmonary bypass (CPB) is associated with AKI [3-6]. Pediatric patients with cyanotic congenital heart disease undergoing CPB are at increased risk for developing AKI [7-9]. The pathophysiology of CPB-related AKI include renal hypoperfusion, ischemia-reperfusion injury and CPB-induced systemic inflammatory response with activation of the blood cascade systems [2]. The complement system is one of the initiators of the systemic inflammation. The cause of systemic inflammatory response syndrome (SIRS) is the contact between blood components and CPB artificial surfaces. This contact is perceived as a danger signal by the body [10]. Other danger signals, and hence SIRS contributors, are ischemia-reperfusion, surgical trauma, and probably endotoxemia. The danger signals activate leukocytes and endothelial cells as well as the plasma cascade systems [11]. The blood cascade systems are comprised by the coagulation, fibrinolytic, kallikrein-kinin, and complement systems. In SIRS there is an unproportional activation of these systems, which is harmful to patients especially in those who have other risk factors. These cascade systems are mutually correlated and “cross talk” to each other. This means that activation of one system may lead to the activation of the other systems [12, 13].

### **1.3 Diagnosis of AKI**

The diagnosis of AKI is based on clinically and laboratory variables like decreased urine output and increased serum creatinine (the cornerstone of the AKI) [14]. However, the fact that creatinine is a late marker of AKI, has led to a considerable search for other

biomarkers enable to early predict the proceeding AKI. Early prediction of AKI is important for timely initiation of prophylactic treatment options. One promising biomarker is NGAL [15].

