4.2 Concomitant treatments and medications

4.2.1 Treatments and medication in OR

- Weaning of CPB: Only include the box “extra bolus study drug”
- Inotropic score (calculated value in CRF)
- Other medication (OR only):
 - Betablocker (YES/NO),
 - Furosemide (YES/NO),
 - Cortisone (YES/NO),
 - Cyklokpron (YES/NO),
 - Fibrinogen (YES/NO),
 - Other medication (YES/NO)
- Fluid balance (OR only):
 - Albumin (YES/NO),
 - Plasma (YES/NO),
 - RBC (YES/NO),
 - Thrombocytes(YES/NO),
 - Diuresis (in ml)

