4.2.2 Treatments and medication in ICU

Concomitant medications will be presented per day (Medications in the ICU on the operative day (Status and medication_1), postop day 1 (Status and medication_2), postop day 2 (Status and medication_3), postop day 3 (Status and medication_4), postop day 4 (Status and medication_5)) and postop day 1+2 and at any time.

- Albumin infusion (Yes (>0 ml)/No(0 ml))
- Trombocyte transfusion (Yes (>0 ml)/No(0 ml))
- RBC (Yes (>0 ml)/No(0 ml), RBS in CRF miss spelling)
- Plasma (Yes (>0 ml)/No(0 ml))
- Betablocker (Yes/No)
- Cordarone (Yes/No)
- Furosemide (Yes/No)
- Furosemide (mg)
- Ethacrynic acid (Yes/No)

STATISTISKA KONSULTGRUPPEN		Statistical Analysis Plan	
Protocol: The prophylactic effect of Levosimendan in reducing acute kidney injury postoperatively in pediatric patients undergoing corrective heart surgery		Protocol No: MiLe-1	Version: 1.0 Page 10 of 17

- Ethacrynic acid (mg) (Reomax in CRF)
- hANP (Yes/No)
- Spironolactone (Yes/No)
- Spironolactone (mg)
- Methylprednisolone (Yes/No)
- Hydrocortisone (Yes/No)
- Betametason (Yes/No)
- Cortisone: Methylprednisolone, Hydrocortisone or Betametason (Yes/No)
- NO (Yes/No)
- Other medication (free text)
- Dialysis (Yes/No)
- NSAID (Yes/No, Search text Other specify field, Comments field, Extra comments and Important information:info_other_comments for NSAID, Ibuprofen, Brufen) (listing only)
- Vancomycin (Yes/No, Search text field Other specify field, Comments field, Extra comments and Important information:info_other_comments for Vancomycin, Vancocin) (listing only)
- Use of contrast (Yes/No from Important information) (listing only)
- Study drug in the PICU (Study drug in CRF):
 - Study drug according to protocol (YES/NO),
 - Milrinone started (YES/NO)

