4.4.3 Secondary endpoints Follow up postop days 1-4

Fluid balance

- Fluid balance ((ml)
- Urine (ml)
- Weight (g)
- %FO (fluid balance (ml)/1000_(+24 hours) /preop weight (kg)) x 100. For example for day 1 the Fluid balance measured at day 2 will be used. If a negative fluid balance set %FO to 0.
- Cumulative %FO (day 1+2, day 1+2+3, day 1+2+3+4)

STATISTISKA KONSULTGRUPPEN		Statistical Analysis Plan	
Protocol: The prophylactic effect of Levosimendan in reducing acute kidney injury postoperatively in pediatric patients undergoing corrective heart surgery		Protocol No: MiLe-1	Version: 1.0 Page 12 of 17

- Peritoneal Dialysis day 1 and day 2 from Status and medication_1 and Status and medication_2

Morning lab results (Postop day 1 is under hemodynamics_1, etc.)

- Hb (g/L)
- Hct
- Leucocytes ($\times 10^9/L$)
- Trombocytes ($\times 10^9/L$)
- C R P (mg/L)
- Albumin (g/L)
- Creatinine ($\mu\text{mol}/L$)
- Corrected creatinine [$(\text{creatinine } (\mu\text{mol}/L) \times [1 + (\text{fluid balance } (L)_{(+24 \text{ hours})} / (\text{weight } (\text{kg}) \times 0.6)])]$ only calculated for day 1-3. For example for day 1 the Fluid balance measured at day 2 will be used. If negative values in fluid balances, fluid balance is set to 0.
- Corrected creatinine (age differentiated), same as above but (in the formula) using 0.75 for infants younger than 5 months and 0.6 for infants/adults older than 5 months.
- AKI_(72 hours) and AKI_(96 hours) in same fashion as in primary endpoint
- AKI stage at 48 (24 and 48), 72 and 96 hours.
 - Stage 0 (no AKI, corrected creatinine up to 1.49 times screening creatinine)
 - Stage 1 (corrected creatinine 1.5-1.99 times screening creatinine)
 - Stage 2 (corrected creatinine 2-2.99 times screening creatinine)
 - Stage 3 (corrected creatinine 3 (or more) times screening creatinine or need of dialysis)
- eGFR Creatinine (calculated value from CRF)
- Cystatin C (mg/L)
- eGFR Cystatin C, calculated using formula $91 \times \text{Cystatin C } (\text{mg/L})^{-1.213}$
- Urea (mmol/L) Use value in database (no recalculation is needed), in CRF the unit stands as $\mu\text{mol}/L$ but it is actually mmol/L.
- Combined eGFR (mL/min per 1,73 m²)
 - $39.1 \times [\text{height } (\text{m})/\text{Serum creatinine } (\text{mg/dl})]^{0.516} \times [1.8/\text{Cystatin C } (\text{mg/L})]^{0.294} \times [30/\text{Urea } (\text{mg/dl})]^{0.169} \times [1.099]^{\text{male}} \times [\text{height } (\text{m})/1.4]^{0.188}$

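### Urine output, a tested secondary endpoint, is specified in absolute ml with no scaling to or adjustment for body weight, which costs precision in infants aged 1 to 12 months

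*Protocol*

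**What the plan says.** Protocol 1.3 says, as background, that AKI is diagnosed "based on clinically and laboratory variables like decreased urine output and increased serum creatinine". The trial's own definition uses creatinine only (Protocol 2.2 and section 3; SAP 4.4.1); SAP 4.4.3 adds dialysis for stage 3.

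SAP 4.4.3 places urine, in ml, under the fluid balance heading of the secondary endpoints for postoperative days 1 to 4. The same list defines percentage fluid overload as "FO (fluid balance (ml)/1000_(+24 hours) /preop weight (kg)) x 100", so that variable is scaled to preoperative weight. Corrected creatinine, also in 4.4.3, uses weight as well.

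SAP 5.5.2 tests secondary continuous outcomes with an independent-groups t-test, or a permutation test if the data are clearly non-normal. Covariance adjustment is foreseen only for the variable's own baseline, and only if the arms differ on it. The baseline lists in SAP 4.1 include preoperative weight but no urine output.

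Among the concomitant treatments, operating-room diuresis is recorded as "Diuresis (in ml)" in SAP 4.2.1. Diuretics in SAP 4.2.2 are recorded as "Furosemide (mg)", "Ethacrynic acid (mg) (Reomax in CRF)" and "Spironolactone (mg)", each alongside a yes/no item. These are to be presented by day.

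The population is described as "Young children, between the age of 1 to 12 months, with congenital heart disease" (Protocol synopsis).

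**The concern.** Urine volume in ml is the product of body weight and output per kg. Only output per kg says anything about the kidney. Two infants with the same renal function but different weights give different volumes, and an unadjusted test on ml treats that difference as unexplained variation. A real difference between arms in urine output is then harder to detect.

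The own-baseline adjustment cannot help, because the baseline lists contain no urine value to adjust for. The SAP scales a neighbouring variable by weight and gives no reason for treating urine differently.

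A smaller, descriptive issue is that a mean number of milligrams of diuretic per arm, or a mean intraoperative diuresis in ml, mixes how much was used or produced with how large the infants were.

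**Working it through.** **The plan's own figure.** There is none for urine. The only design figure is 70 patients for a 20% reduction in creatinine at 80% power (Protocol 10.1, SAP 1.4), stated without an SD. It does not bear on this point beyond fixing 35 per arm.

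**Inputs from the documents.** 35 per arm; two-sided alpha 0.05 (SAP 5.1); t-test (SAP 5.5.2); age 1 to 12 months.

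**Assumptions, because the documents give no values.**
- CV of urine per kg (CVu): 30, 40 or 50%, lognormal.
- Weight uniform on 3.5-10 kg or on 4-8 kg. Only 3.5 kg appears in the protocol, as the worked example for blood volume in section 8.1.
- Weight and per-kg output independent.
- True effect: one arm's mean 25% below the other's.

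**Illustration.** At an assumed 2 mL/kg/h, a 3.5 kg infant makes 2 × 3.5 × 24 = 168 ml/day and a 10 kg infant makes 2 × 10 × 24 = 480 ml/day, with identical output per kg.

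**Weight CV (CVw).** For a uniform range, SD = range/√12.
- Wide: (6.5/√12)/6.75 = 1.876/6.75 = 0.278.
- Narrow: (4/√12)/6 = 1.155/6 = 0.192.

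**Variance on the ml scale.** For a product of independent variables, CVml² = (1 + CVw²)(1 + CVu²) − 1. For example, wide range with CVu 0.30: 1.0773 × 1.09 − 1 = 0.174, against 0.090 per kg, a ratio of 1.94. The share of variance added by weight is 1 − 1/ratio.

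Power is by simulation (20,000 trials per setting) and is good to about one point.

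| Weight range | CVu | CVu² | CVml² | Ratio | Share from weight | Power per kg | Power in ml | Loss (points) |
|---|---|---|---|---|---|---|---|---|
| 3.5-10 kg | 0.30 | 0.090 | 0.174 | 1.94 | 48% | 98% | 81% | 17 |
| 3.5-10 kg | 0.40 | 0.160 | 0.250 | 1.56 | 36% | 84% | 66% | 18 |
| 3.5-10 kg | 0.50 | 0.250 | 0.347 | 1.39 | 28% | 66% | 53% | 13 |
| 4-8 kg | 0.30 | 0.090 | 0.130 | 1.45 | 31% | 98% | 91% | 7 |
| 4-8 kg | 0.40 | 0.160 | 0.203 | 1.27 | 21% | 84% | 75% | 9 |
| 4-8 kg | 0.50 | 0.250 | 0.296 | 1.19 | 16% | 66% | 59% | 7 |

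**Wider grid.** With CVw 0.15-0.35 and CVu 0.30-0.60, the ratio runs from 1.08 to 2.48. In the middle case (0.25, 0.40) it is 1.45, equivalent to an effective 35/1.45 ≈ 24 per arm. Weight supplies more than half the variance only where CVw is at least as large as CVu.

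**Type I error.** With no treatment effect, the t-test on ml rejected in 4.8% (CVw 0.25, CVu 0.40) and 4.9% (0.35, 0.30) of 20,000 simulated trials.

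**The case against.** The strongest reply is that this is one supportive variable among dozens and that randomisation already protects it. Much of that stands.

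- A reader might infer that body weight swamps or biases the comparison. The figures do not support this. Type I error holds at its nominal level, and in the main table weight never supplies most of the variance. Randomisation is stratified by age as well as diagnosis (Protocol 4.3.1), and age is a partial proxy for weight, so no systematic weight imbalance is expected. Stratification does not, however, remove within-arm weight variation from an unadjusted test.
- A reader might infer that the SAP contradicts the protocol's diagnosis of AKI. It does not. The sentence in 1.3 is background, and urine is in neither the primary endpoint nor the AKI stages.
- A reader might infer that diuretic doses are tested between arms in mg. SAP 4.2.2 only presents them by day, no test of dose is specified, and the yes/no items need no scaling.
- Urine is not the only sign of AKI outside the biomarkers. Weight-scaled fluid overload and dialysis are also recorded.
- The size of the loss rests on assumed CVs, weights and effect. If heavier infants produce less per kg, the penalty shrinks.

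What remains is that a tested endpoint related to renal function is set on a scale that includes body size, and no other part of the SAP corrects for it.

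**Conclusion.** The point holds as a loss of precision in one secondary endpoint. Under the stated assumptions, analysing ml instead of ml per kg raises the squared CV 1.2 to 1.9 times and costs about 7 to 18 points of power for a 25% difference at 35 per arm. The existence of a loss needs only that weight varies and that per-kg output is roughly unrelated to it. Its size depends on the assumed distributions and should be read as a range. The primary endpoint, the type I error and the validity of the randomised comparison are unaffected. For intraoperative diuresis and the diuretics, the issue is only how readable the descriptive tables are. This is a low-stakes change, worth making because it is so cheap and matches how the SAP already treats fluid overload.

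**What to change.** - **SAP 4.4.3:** replace urine in ml with urine output per kg of preoperative weight, in mL/kg/h, or mL/kg per 24 h if collection hours are not recorded. Make this the variable tested under 5.5.2. Adding preoperative weight as a covariate is an acceptable alternative, and is preferable if per-kg output is itself thought to vary with weight.
- **SAP 4.2.1 and 4.2.2, descriptive tables only:** also show operating-room diuresis in mL/kg and furosemide, ethacrynic acid and spironolactone in mg/kg/day. This concerns reporting units, not treatment.

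The cost is a few lines of SAP text and some derived variables. Preoperative weight is already collected (SAP 4.1.2). There is no new data collection, no effect on patients and no effect on sample size. The change should be made before unblinding, so that the choice of scale cannot depend on the results.

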## **1.4 Prevention of AKI**

There is no causal treatment for AKI, highlighting the importance of the preventive measures. As mentioned previously, renal hypoperfusion is one of the etiologies to AKI. In this study we aim to intervene renal hypoperfusion (by Levosimendan).

## **1.5 Levosimendan**

### **1.5.1 Mechanism of action**

Levosimendan belongs to a relatively new group of drugs which is called calcium-sensitizing. Levosimendan enhances the contraction of heart muscle fibers at the same level of cytosolic calcium concentration. It performs this by holding the calcium-binding site of troponin C in its active conformation which leads to more binding at lower intracardiac calcium concentrations. The advantage of this approach, compared with other inotropes, is the needlessness of increased cytosolic calcium. Hence, the negative effects of increased cytosolic calcium on oxygen consumption and mitochondrial function can be avoided in addition to the avoidance of the activation of various calcium-dependent proteases and phospholipases which mediate systemic inflammation during ischemia-reperfusion. Levosimendan also stimulates membrane potassium-sensitive adenosine triphosphate (KATP) channels. This leads to dilation of peripheral and coronary vessels. Levosimendan also stimulates the same channels in mitochondria and opens them, which may be an important mechanism of pharmacologic preconditioning and cytoprotection. Levosimendan differs from other inotropic agents like dopamine, amrinone, and Milrinone, with regard to maintaining the positive inotropic properties even in the abnormal myocardium. Levosimendan mechanism of action indicates limited, if any, potential to initiation of arrhythmias, which is confirmed by clinical experience. At much greater concentrations, it does inhibit phosphodiesterase III (like Milrinone), but this effect does not appear to be relevant at clinical concentrations [16].

